3.4.3. Exploratory Efficacy Measures

The following exploratory efficacy measures will be collected at the times shown in the Protocol:

- Functional status assessed by the SF-36:
 - The SF-36 is a 36-item, subject-reported measure yielding 8 subscale scores (Vitality, Physical Functioning, Bodily Pain, General Health Perceptions, Physical Role Functioning, Emotional Role Functioning, Social Role Functioning, and Mental Health) and 2 component summary scores (Physical Functioning and Mental Functioning)
- Pain assessed by the BPI-SF questionnaire:
 - The BPI-SF is a 9-item self-administered questionnaire used to evaluate the severity of a subject's pain and the impact of this pain on the subject's daily functioning on an 11-point scale (ie, 0 = "no pain" to 10 = "pain as bad as you can imagine")

• Exploratory biomarkers for Gaucher disease in serum, plasma, PBLs, and urine: as knowledge of Gaucher disease pathophysiology and related biomarkers continues to evolve, serum, plasma, peripheral blood and urine samples will be collected and archived for possible future non-genomic and genomic biomarker testing.

3.4.4. Safety Measures

3.4.4.1. Primary Safety Measures

Primary safety evaluations to be performed during the study include monitoring of adverse events (AEs) and concomitant medications, clinical laboratory evaluations including hematology, serum chemistry, and urinalysis, measurement of vital signs, 12-lead electrocardiograms (ECGs), and physical examinations.

3.4.4.2. Exploratory Safety Measures

Exploratory safety evaluations to be performed during the study include assessments of reproductive potential.

4. PLANNED ANALYSES

4.1. Interim Analysis

In this open-label study, after AVR-RD-02 infusion, measures of engraftment, clinical response, and safety are assessed for each individual subject on an ongoing basis. Also, based on stopping rules and safety data collected from initial enrolled subjects, an independent DMC review at pre-specified intervals will assess the appropriateness of the progressive introduction of additional cohorts and subjects.

Considering this, a discrete interim analysis of data collected in this study will not be performed.

4.2. Final Analysis

The final database lock will occur when all subjects have completed the study (i.e., the final followup visit at Week 52 [or prematurely discontinued the study]) and all data are collected and cleaned.

5. GENERAL CONSIDERATIONS FOR DATA ANALYSES AND HANDLING

5.1. General Summary Table and Individual Subject Data Listing Considerations

Summary tables and listings will be prepared according to ICH Guideline E3.

The All Subjects population will be used for specific outputs, as defined below. Safety data will be reported using the Safety and Infused populations, and Efficacy data will be reported using the Infused population.

No treatment-naïve subjects were enrolled, so outputs will only contain switch-stable subjects.

Summary tables for any concomitant medications will be coded according to the World Health Organization (WHO) Drug dictionary Version of WHODrug Global B3 March 2018. Adverse event preferred terms and body/organ systems and medical history conditions will be coded using the Medical Dictionary for Regulatory Activities (MedDRA[®]) dictionary Version 23.0.

Missing data will be reported as follows:

- Data captured as 'Unknown', or variations thereof, in the clinical database will be presented as such in the Listings
- Missing data and will be displayed as follows in Listings:
 - 'Not Done' will be presented where a sample was not collected/assessment was not performed (as per EDC)
 - 'No Result' will be presented where the sample was collected/assessment was performed (as per EDC) but no result is available.
 - 'Not Applicable' will be presented when the sample/assessment was not required/expected for that subject/visit, e.g., where a result would only be expected after a protocol amendment but not prior to that amendment.
 - 'Not Calculated' will be presented when no result can be derived, e.g., standard deviation is NC when n<3, or change from baseline (CFB) is NC when no baseline or post-baseline result is available.
- If all data for a specific visit are missing the data are included in the table with N=0.
- Safety assessment values of the form of "< x" (i.e., below the lower limit of quantification (BLQ)) or "> x" (i.e., above the upper limit of quantification) will be imputed as "x" in the calculation of descriptive statistics but displayed as "< x" or "> x" in any listings that are produced.
 - If the calculated mean at a sampling time point is BLQ then the mean value will be reported as 'BLQ' and the SD and CV% will be reported as not calculated (NC) in the summary.
 - Similarly, any calculated BLQ values for median, minimum, maximum and geometric mean will be reported as 'BLQ' in the summary.
 - If the calculated mean at a sampling time point is above ULQ then the mean value will be reported as '>ULQ' and the SD and CV% will be reported as not calculated (NC) in the summary.

• Similarly, any calculated values for median, minimum, maximum and geometric mean will be reported as '>ULQ' in the summary.

Imputed dates and times will NOT be presented in the listings. Completely missing start or end dates/times will remain missing, with no imputation applied. Consequently, time to onset and duration of such events will be missing. Partial dates/times will be displayed as captured in subject listing displays.

5.2. General Post Text Summary Table and Individual Subject Data Listing Format Considerations

The tables and listings will be numbered using a decimal system to reflect main levels of unique tables and listings and sub-levels of replicate tables and listings with two digits per level (e.g., Table XX.YY.ZZ. ...).

1. The first level number will be consistent with the corresponding Clinical Study Report (CSR) appendix in which the tables or listings will appear. For example, the post text tables will appear in Appendix 14 (and will be numbered 14.XX.YY) and the individual subject data listings will appear in Appendix 16 (and will be numbered 16.XX.YY). The subject disposition table will be first in the first section of the report and will be numbered Table 14.1. The supportive subject data listing will be Listing 16.1. Any subset table will have the number Table 14.1.2, etc.

2. Table numbering will follow ICH E3. Subject disposition, baseline and demography and prior and concomitant medications tables should appear as the second level number (Table 14.1 series). Efficacy tables will occupy the next sub-level (Table 14.2 series). Safety tables will follow next (Table 14.3 series). Similar conventions will be applied to the subject data listings.

3. Each table and figure title will be complete, accurate and concise. The last line of the title will provide the analysis population being summarized/presented.

4. All analysis and summary tables will include the analysis population sample size (i.e., number of subjects).

5. Each listing title will be complete, accurate and concise. Inclusion in each analysis population will be presented as a flag on selected listings.

6. If possible, variables being summarized and statistics reported will appear in the left most column of a table.

5.3. Data Management

All data will be recorded by the site in individual source documents. An eCRF will be created by the data management group for recording of the required data in the study database. All eCRF information is to be filled in by site staff. If an item is not available or is not applicable, this fact should be indicated, where possible. Blank spaces should not be present unless otherwise directed.

All information recorded in the eCRFs for this study must be consistent with the investigator's source documentation for the study participants. The investigative site will make available source documents to any personnel monitoring the study. The study monitor will verify consent of all subjects to participate in the study and will perform 100% source data verification (SDV) of data

entered into the eCRF and raise queries as needed for correction by the site. The data entered into the eCRF will be subject to data validation checks for consistency and completeness by the data management group. Data queries will then be generated as needed and sent to the investigational site for response before the database is locked and released for statistical analysis.

Data from any screen failures is entered into the clinical database, but this data might not be cleaned. In order to describe the representativeness of the study, this data should be presented including the reasons for screen failures (failure of individual inclusion/exclusion criteria could be presented if appropriate).

Data storage, data transfer and data validation will be conducted according to the relevant Standard Operating Procedures (SOPs).

Following database lock, data will be shared with the AVROBIO, Inc. Biostatistics Department for programming of analysis datasets, tables, listings, and figures. All SAS[®] programs used to create analysis datasets and outputs will be validated by ensuring that the ".log" files are void of all errors, warnings, and notes indicative of problems. Additionally, each program will be checked to ensure that it performs according to the program specification. All programs will be developed and validated through risk-based quality control by the AVROBIO, Inc. Biostatistics Department.

Outputs will include data extraction date. The purpose of the data extraction date is to link the output to the database, either active or archived, that is write-protected for replication and future reference. The program execution date will appear on each output page and will indicate the date the output was generated by the analysis program. Individual source listings will display all the relative values supporting corresponding table(s) and figure(s).

Vendor Name	Assay	Parameter (Units)	LLD ¹	LLQ ¹	ULQ ¹	LLN ¹	ULN ¹
	GCase enzyme activity (PBLs)	µmol/g/h	NA	0.3	100.0	4.0	NA
	GCase enzyme activity(plasma)	µmol/L/h	NA	0.2	200.0	0.4	NA
	GCase enzyme activity (DBS µ card)	µmol/g/h	NA	1.0	200.0	4.1	NA
	Chitotriosidase Enzyme Activity	µmol/L/h	NA	0.8	150.0	NA	38.1
	Lyso-Gb1 (plasma)	ng/mL	NA	0.6	1000.0	NA	1.2
	GBA gene sequence	NA ²	NA	NA	NA	NA	NA
	CHIT1 gene sequence	NA ²	NA	NA	NA	NA	NA

Table 2: Laboratory data vendors

	VCN (peripheral blood)	average copies/cell	NA	0.0027	NA	NA	0.0
	anti-GCase antibody titer	ng/mL	5.33 ³	15.9 ³	NA	NA	0.0
	Replication competent lentivirus	NA ²	NA	NA	NA	NA	NA
	Insertion site analysis	NA ²	NA	NA	NA	NA	NA

¹LLD = Lower Limit of Detection; LLQ = Lower Limit of Quantification; LLN = Lower Limit of Normal; ULN = Upper Limit of Normal

² This method does not generate quantitative results.

³Sensitivity was established both for screening and confirmatory runs. The LLD represented the lower limit used for the screening run. The LLQ represents the lower limit used for the confirmatory run. This arrangement reduces the potential for type I errors.

5.4. Data Presentation Conventions

The following conventions will apply for data presentation:

- All listings will be produced using the All Subjects population;
- Continuous safety variables will be reported to the same precision as the source data. Derived variables will be reported using the same precision as the value(s) from which they were derived. For the reporting of descriptive statistics, the mean, median, standard deviation and CV% will be reported to 1 decimal place more than the source data; the minimum and the maximum values will be presented to the same precision as the source data;
- For categorical/discrete variables, the frequency count and the percentage (of available data) for each category of the variable will be presented and will be displayed in the form XX (XX.X%) where the percentage is in the parentheses. The denominator for all percentages will be the number of subjects with non-missing data within the analysis population of interest. Otherwise, percentages (for example for AEs and Concomitant Medications) will be calculated based on the population total. If the analysis population is not stated in the title then a footnote will clarify the denominator used. A row denoted 'Missing' will be included in count tabulations to account for dropouts and missing values;
- All percentages will be rounded to one decimal place. In the case the numerator is equal to the denominator, the percentage should be presented as (100) instead of (100.0). In the case the numerator is equal to 0, the percentage will not be presented;

- Date variables will be formatted as DD-MMM-YYYY for presentation. Time will be formatted in military time as HH:MM for presentation;
- Unscheduled assessments will be considered when applying visit windows and derived study periods and will also contribute to the end of study value, or best/worst case value where required (e.g., shift table);
- When deriving a subject level statistic (e.g., maximum value post-baseline), all values should be included regardless of whether they appear in a corresponding visit-based summary;
- All listings will be sorted for presentation in order of subject, parameter, and date/time of procedure or event.
- Individuals who do not meet the criteria for participation in this study (screen failure) may be re-screened once upon discussion between the Investigator and Medical Monitor.
 - Where a re-screened subject is present in the clinical database under two different identifiers, data will be combined for Tables and Figures, and the identifiers will be concatenated for Listings with a footnote included to describe the details of re-screening.
- For medical/surgical history and AEs, frequency ordering will be used for the summary table presentation (i.e., order by the overall grouping in descending frequency, and then alphabetical order in the case of equal frequency, for each System Organ Class (SOC) and also for each Preferred Term (PT) within each SOC). Columns that are used for grouping in descending frequency will be specified in the footnote;
 - TEAEs will be presented in descending order of frequency across all subjects.
- Outputs will define Lower Limit of Quantification (LLQ) and Upper Limit of Quantification (ULQ) values, including the units, if applicable;
 - Values below the LLQ (BLQ), or not detected or not quantifiable, will be imputed as the LLQ (where available) or as 0.01 for figures and for summary statistics, and n imp, the number of imputed values, will be reported;
 - Values above the ULQ will be imputed as the ULQ (where available) for figures and for summary statistics, and n imp, the number of imputed values, will be reported;
 - Imputed values will be used for Tables and Figures, but Listings will present the original values
- Outputs will define Lower Limit of Detection (LLD) values, including the units, if applicable;
- Outputs will include reference ranges and Normal Ranges, including the units, if applicable;
- Outputs will include units, if applicable;

- On all plots with time on the x-axis, the spacing of the x-axis timepoints will be on a continuous scale and will reflect actual time between visits, if spacing permits;
- On all plots, where a mean line is included, a dashed black line (thickness greater than the individual subject lines) will be used;
- A month is counted as 30.4375 days and a year is counted as 365.25 days (30.4375 days × 12 months);
- Summary statistics:
 - Summary statistics for efficacy data (absolute values) will include N, n, geometric mean, coefficient of variation between subjects (%CVb), median, minimum, and maximum will be reported (where n<3, only mean, median, minimum and maximum will be presented);
 - Geometric Mean will be presented when at least 3 values (including imputed values) are available;
 - %GeoCV will be calculated as: $100 * (e^{sd(log(X))} 1);$
 - Summary statistics for safety data, and for changes from baseline, will include N, n, mean, SD, minimum, median, and maximum will be reported (where n<3, only mean, median, minimum and maximum will be presented);
- For plots of log-normal data, the y-axis may be presented on the log-scale, as required;

Outputs will be delivered as pdf and rtf format.

5.5. Analysis Populations

Subject inclusion into each population will be determined before database lock and prior to commencing the final analysis.

5.5.1. All Subjects Population

The All Subjects population will consist of all subjects who consented, i.e. were enrolled.

All listings will be produced using the All Subjects population.

5.5.2. Safety Population

The Safety population will consist of all enrolled subjects who receive any auxiliary medication (G-CSF, plerixafor, busulfan, or anti-convulsant) or AVR-RD-02. This population will be used for the summaries of all safety data.

5.5.3. Infused Population

The Infused population will consist of all enrolled subjects who receive all auxiliary medications and AVR-RD-02. This population will be used for the summaries of all efficacy and safety data.

5.6. Baseline Definition

For all **safety and efficacy endpoints**, Baseline (Derived) will be defined as the last available, nonmissing observation prior to first administration of an auxiliary medication (G-CSF, plerixafor, busulfan, or anti-convulsant) or AVR-RD-02, unless specifically mentioned otherwise.

Non-numeric (i.e., categorical) observations will be considered for baseline calculations, where applicable. In addition, non-missing results from unscheduled assessments prior to first administration of an auxiliary medication may also be considered in the calculation of baseline observations.

If more than one assessment is collected first administration of an auxiliary medication or AVR-RD-02 infusion and it is not possible to determine which is the closest then the mean of the assessments will be used as Baseline (Derived).

Where baseline values are at or below the LLQ (BLQ), or not detected or not quantifiable, these will be imputed as the LLQ (where available) or as 0.01 for figures and for summary statistics.

Likewise, values above the ULQ will be imputed as the ULQ (where available) for figures and for summary statistics.

Baseline (Derived) will be defined as a footnote on each applicable output.

Listings, Tables and Figures will present all visits and Baseline (Derived), however, figures and shift tables presenting change from baseline (CFB) or percent change from baseline (%CFB) will only include Baseline (Derived) and post-baseline visits only.

5.7. Derived and Transformed Data

The SAP includes all derivations that are necessary for the analysis and reporting of the study. Any handling rules for source data (from the eCRF or from a third-party vendor) and derived data are detailed in this SAP. Any endpoints that already have the derivation performed in the source data, and therefore need no further programmatic derivation, are identified as such.

5.7.1. Age at Screening

Age, in completed years, at screening will be defined as:

Age (years) = floor value ((Date (first) signed Informed Consent – Date of Birth + 1) / 365.25)

5.7.2. Body Mass Index

Body Mass Index $(kg/m^2, to one decimal place) = Body Weight (kg) / (Height x Height (m))$

5.7.3. Study Day

Study Day will be defined as:

Study Day = Date of Assessment – Date of AVR-RD-02 infusion (if date of assessment is before Date of AVR-RD-02 infusion)

Otherwise, Study Day = (Date of Assessment – Date of AVR-RD-02 infusion) + 1 For any population which includes subjects who may not have received AVR-RD-02, e.g., the Safety population, the Study Day will not be derived, except where the SAP indicates date of (first) signing of informed consent is used.

5.7.4. Study Week

Study Week will be defined as:

Study Week = floor value [(Study Day / 7) + 1]

5.7.5. Time since AVR-RD-02 Infusion

Time since AVR-RD-02 infusion will be calculated as:

Time Since AVR - RD - 02 (*months*) = $\frac{Study Day}{30.4375}$

5.7.6. Age at enrollment

Age at enrollment will be calculated as:

$$Age \ at \ Enrollment \ (months) = \frac{(Date \ of \ (first) \ Informed \ Consent - Date \ of \ Birth)}{30.4375}$$

5.7.7. Age at AVR-RD-02 infusion

Age at AVR-RD-02 infusion will be calculated as:

$$Age \ at \ AVR - RD - 02 \ Infusion \ (months) = \frac{Date \ of \ Infusion - Date \ of \ Birth}{30.4375}$$

5.7.8. Adverse event onset time relative to AVR-RD-02 infusion

Adverse event onset time relative to AVR-RD-02 infusion will be calculated as:

Adverse event onset time relative to AVR-RD-02 infusion = Onset Date and Time of AE – AVR-RD-02 infusion Date and Time, if onset date of AE is before Date of AVR-RD-02 infusion

Otherwise, Adverse event onset time relative to AVR-RD-02 infusion = (Onset Date and Time of AE - AVR-RD-02 infusion Date and Time) + 1

Where time is missing, only dates will be used. Refer to Section 5.7.15 for handling of incomplete dates.

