5.7.9. Duration of Adverse Events

Duration of Adverse Events (in DD:HH:MM) will be calculated as:

Duration of Adverse Event = (Resolution Date and Time) – (Onset Date and Time)

Where time is missing, only dates will be used. If a resolution or onset date is missing or incomplete, no duration will be derived.

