The date and time of AEs are captured, as well as date and time for G-CSF, plerixafor, apheresis, busulfan and AVR-RD-02 infusion. Therefore, when assigning AEs to a study period, the time (HH:MM) of the onset (or worsening) of the AE will be compared to the time of the auxiliary medication or AVR-RD-02, e.g., on Day 1, an AE with onset time prior to the start time of AVR-RD-02 infusion will be assigned to the Conditioning study period. Where time is missing or incomplete, the AE will be assigned to the study period using the date alone, e.g., on Day 1, an AE on Day 1 with onset time missing will be assigned to the AVR-RD-02 infusion study period.

If an adverse event continues into subsequent periods it will only be counted in the period in which it first occurred, in order to avoid double counting.

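### SAP 5.7.8 adds a Study Day +1 to a date-and-time difference, so AEs timed earlier on the infusion date get a positive onset time relative to infusion

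*SAP*

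**What the plan says.** SAP 5.7.8 has two branches. The plain date-and-time difference applies "if onset date of AE is before Date of AVR-RD-02 infusion". Every other AE takes the second branch, "Onset Date and Time of AE - AVR-RD-02 infusion Date and Time) + 1". Clock time is dropped only in one case: "Where time is missing, only dates will be used". The section gives no unit.

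Three neighbouring sections bear on this:

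- **SAP 5.7.3** defines Study Day from dates alone: "Otherwise, Study Day = (Date of Assessment – Date of AVR-RD-02 infusion) + 1". The infusion date is therefore Day 1.
- **SAP 5.7.9** defines AE duration as a date-and-time difference with nothing added: "Duration of Adverse Event = (Resolution Date and Time) – (Onset Date and Time".
- **SAP 5.7.15** confirms that clock times are collected: "The date and time of AEs are captured, as well as date and time for G-CSF, plerixafor, apheresis, busulfan and AVR-RD-02 infusion". It also covers the AE that starts on the infusion day before the infusion does: "an AE with onset time prior to the start time of AVR-RD-02 infusion will be assigned to the Conditioning study period".

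**The concern.** The +1 suits a whole-day count that has no day zero, as in 5.7.3. In 5.7.8 it is added to a quantity that already carries hours and minutes. Because the branch depends on the date only, an AE that begins on the infusion date but before the infusion takes the +1 branch and can come out positive. The same event is then before infusion by study period and after infusion by onset time.

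The ordering is of interest on that day. Under Protocol 8.1.2 the infusion follows the end of the last busulfan infusion by 24 to 48 hours, and Protocol 8.3.2 lists reactions that stem cell infusion can cause. Conditioning toxicity and an infusion reaction can therefore fall on the same date. With AE and infusion times both captured, the date-and-time calculation is the normal route, not a rare exception.

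**Working it through.** The plan gives no worked value to reproduce, so the rule was applied literally to test onsets.

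**Inputs**
- Branch rule and formula: SAP 5.7.8.
- Unit: not stated. Days is assumed, by analogy with 5.7.3; hours is checked as the alternative.
- Infusion start: 12:00, assumed for illustration.
- Period assignment: SAP 5.7.15.

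**Formulas** (days)
- Elapsed time = (onset date/time - infusion date/time) / 24 h.
- 5.7.8 value = elapsed time if the onset date is before the infusion date; otherwise elapsed time + 1.

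**Worked cases**
- 09:00 on the infusion date: -3/24 = -0.125; -0.125 + 1 = +0.875, which reads as 21 h after infusion.
- 12:30 on the infusion date: 0.5/24 = 0.021; 0.021 + 1 = 1.021, which reads as 24.5 h.

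| AE onset | Elapsed (days) | 5.7.8 value (days) | 5.7.8 value in hours | Side of infusion under 5.7.15 |
|---|---|---|---|---|
| 23:59, day before | -0.501 | -0.501 | -12.02 | before |
| 00:01, infusion date | -0.499 | +0.501 | +12.02 | before |
| 09:00 | -0.125 | +0.875 | +21 | before |
| 11:30 | -0.021 | +0.979 | +23.5 | before |
| 12:30 | +0.021 | +1.021 | +24.5 | after start |
| 15:00 | +0.125 | +1.125 | +27 | after start |
| 12:00, next day | +1.000 | +2.000 | +48 | after start |

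Three things follow.

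1. Each timed pre-infusion AE on the infusion date gets a value between 0 and 1. Its sign contradicts the period that 5.7.15 gives it.
2. The value jumps by about one day at midnight: two onsets 2 minutes apart get -0.501 and +0.501.
3. As an elapsed time, each timed AE on or after the infusion date is one day too late.

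**Dates only.** With time missing, an AE on the infusion date gets 0 + 1 = 1, which equals Study Day 1. The rule is coherent there.

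**If the +1 meant one hour.** An AE 3 h before infusion gives -3 + 1 = -2 h, so the sign is right. One 30 min before gives -0.5 + 1 = +0.5 h, so the sign is wrong. One 10 min after gives 1 h 10 min. Only AEs within the last hour before infusion change sign, but every value on this branch is still off by one unit.

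**After removing the +1 when times are known.** 09:00 gives -0.125 and 12:30 gives +0.021, and all signs agree with 5.7.15.

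**The case against.** The best defence is that the +1 is simply the Study Day convention, so that 1.021 means some time on Day 1 and not 24.5 elapsed hours. For AEs after infusion that reading is possible. It does not rescue the rule: the variable is named an onset time, it uses clock times, and values between 0 and 1 have no meaning on a Study Day scale.

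The stronger objection concerns consequence. A reader might infer that the error reaches the primary safety endpoint of AE incidence and severity. The documents do not support that:

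- Tables by onset and by causal relationship use study period (SAP 10.1.1.8), which 5.7.15 assigns by clock time.
- Treatment emergence is anchored to the start of G-CSF (SAP 5.7.15).
- Severity tables use CTCAE grade.
- Cumulative AE plots use study day.

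A reader might also infer that short onset times are lost, or that causality assessment is distorted. Neither follows. AE onset date/time is listed (SAP 10.1.1.8), as are infusion start and end date/time (SAP 8.6). Relatedness to each treatment is the investigator's assessment (Protocol 9.2.1.3), not a product of this variable.

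These limits stand. So does the context: the study was discontinued early, no hypothesis tests are planned, and the SAP is written for an abbreviated report. What remains is a derivation that gives a wrong value as written and that no other section corrects. It is not idle text. SAP 5.7 describes its derivations as those needed for analysis and reporting, and SAP 5.1 refers to time to onset, although no output is expressly tied to 5.7.8.

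**Conclusion.** The defect is real and narrow. If the unit is days, any timed AE earlier on the infusion date gets a positive value between 0 and 1, in conflict with its assignment to Conditioning, and every timed AE on or after that date is overstated by one day as an elapsed time. The 24-hour size depends on the unit being days, which 5.7.8 does not say; the 12:00 infusion start only illustrates it. The effect stops at the derived onset-time variable and any listing or narrative that quotes it. No AE count, grade, treatment-emergence flag or study-period table changes, and the correct elapsed time can be recovered from the listings. With few subjects and reporting mainly by listing, one event shown on the wrong side of infusion could still confuse an individual account, so the correction is worth making.

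**What to change.** In SAP 5.7.8:

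- When both times are known, report AE onset date/time minus infusion start date/time, signed, with no +1. Negative means before infusion. State the unit, and name the start of infusion as the reference, as 5.7.15 does.
- When only dates are known, report Study Day per 5.7.3 as a separate, separately labelled variable, so that elapsed times and day counts never share a column.

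The cost is about one line of SAP text and one derivation. No additional data are needed, because the times are already captured.
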